9.2.4. Safety Evaluations

Details regarding the IDMC are provided in Section 11.13, [Independent Data Monitoring Committee](#).

The study will include the following evaluations of safety and reactogenicity according to the time points provided in the Schedule of Activities:

- Adverse Events
- Vital Signs
- Physical Examination
- Patient-reported Outcomes

9.2.4.1. Adverse Events

AEs will be reported as specified in Section 12, Adverse Event Reporting. Any clinically significant abnormalities persisting at the end of the study/early withdrawal will be followed by the investigator until resolution or until a clinically stable condition is reached.

All Participants

For all participants, SAEs will be collected from administration of study vaccine on Day 1 until the end of the first RSV season (or 6 months after vaccination, whichever comes later).^a

For all participants, some subsets of SAEs will be collected for additional study periods^a:

- ARIs and complications related to ARIs that classify as SAEs will be captured and will be reported as SAEs in the eCRF for the duration of the second RSV season, between the second and the third RSV season, and for the duration of the third RSV season.
- From the time of vaccination until the end of the study period for each participant, SAEs classified as related to the study vaccine, SAEs resulting in death, and (S)AEs leading to discontinuation from the study will be collected.
- During the entire study, (S)AEs and special reporting situations related to study procedures or to non-investigational (concomitant) Janssen products will be reported from the time a signed and dated informed consent form (ICF) is obtained onwards until the end of the study period for each participant.

The (S)AE listing in the eCRF will not be updated based on the RSV RT-PCR results and will remain listed on the eCRF as ARIs.

Safety Subset and Revaccination Subcohorts

These participants will be asked to note in the eDiary occurrences of injection site pain/tenderness, erythema, and swelling at the study vaccine injection site daily for 7 days post-vaccination (Day 1 for the Safety Subset; Day 365 (Month 12)/Day 730 (Month 24)/Day 1,095 (Month 36) for the Revaccination Subcohorts). The extent (largest diameter) of any erythema and swelling should be measured (using the ruler supplied) and recorded daily. The case definitions for solicited injection site events can be found in Gidudu et al.¹¹ and in Kohl et al.¹⁷

Solicited systemic AEs: fatigue, headache, nausea, myalgia, and fever (defined as an endogenous elevation of body temperature $\geq 38.0^{\circ}\text{C}$, as recorded in at least one measurement). Body temperature (oral route preferred) should be measured at approximately the same time each day, preferably in the evening, using the thermometer supplied. If more than one measurement is made on any given day, the highest temperature of that day will be used in the eDiary.

Unsolicited AEs will be collected from the time of vaccine administration through the following 28 days.^b All AEs, including any that are ongoing at 28 days after vaccine administration will be followed until clinical resolution or stabilization. Concomitant therapies associated with

^a The windows for SAE collection in the Revaccination Subcohorts are described below under “Safety Subset and Revaccination Subcohorts”.

^b AEs that start more than 28 days after a vaccination, but that are still present at the time of the next vaccination will also be recorded.

unsolicited AEs will be collected and recorded in the eCRF from time of vaccine administration through 28 days after vaccination.

Relatedness and severity of these events will be graded by the investigator according to the criteria presented in Section 12.1.2 and Section 12.1.3, respectively.

All ARIs and all complications related to ARIs will be reported as AEs in the eCRF from the time of vaccination through the following 28 days for Safety Subset and Revaccination Subcohort participants only.

For Revaccination Subcohort A, all SAEs will be reported from administration of study vaccine on Day 1 until the end of the first RSV season (or 6 months after vaccination, whichever comes later), and from the time of revaccination at Month 12 until the end of the second RSV season, or until 6 months after revaccination, whichever comes later. For Revaccination Subcohort 2A, all SAEs and AESIs will also be collected from the time of revaccination on Day 730 until 6 months after revaccination. For Revaccination Subcohorts B and C, all SAEs and AESIs will be collected from the time of revaccination until 6 months thereafter. Collection of SAEs associated with ARIs and complications related to ARIs that classify as SAEs will stop at the end of the second RSV season for Subcohort A, on Day 730 (Month 24) for Subcohort B, and at the latest at the end of the third RSV season for Subcohort C.

For all Revaccination Subcohorts, SAEs classified as related to the study vaccine, SAEs resulting in death, (S)AEs leading to discontinuation from the study, and (S)AEs and special reporting situations related to study procedures or to non-investigational (concomitant) Janssen products will be collected during the entire study for all participants. For the participants in the Revaccination Subcohort C, these (S)AEs will be collected retrospectively for the time period between the last end of the RSV season visit and the revaccination upon the day of revaccination.

From the time of local approval of protocol amendment 6 onwards, TTS is considered to be an AESI. Thrombotic events and/or thrombocytopenia (defined as platelet count below 150,000 cells/mm³) are considered to be potential AESIs. All AESIs, including potential AESIs, will be reported to the sponsor from the moment of revaccination until 6 months after revaccination.

9.2.4.2. Vital Signs

Blood pressure and pulse/heart rate measurements will be assessed with a completely automated device. Manual techniques will be used only if an automated device is not available.

Vital signs measurements should be preceded by at least 5 minutes of rest in a quiet setting without distractions (eg, television, cell phones).

The following measurements will be performed:

- Heart rate (beats per minutes), respiratory rate (breaths per minute), supine systolic blood pressure (mmHg) and supine diastolic blood pressure (mmHg)

- Body temperature (oral route preferred, or in accordance with the local standard of care)
- Oxygen saturation (SpO₂)

9.2.4.3. Physical Examination

A full physical examination, including body weight, will be carried out before each vaccination. Height will be measured on Day 1 only.

9.2.4.4. Patient-reported Outcomes

Details for PRO assessments in this study are described in Section [9.2.1.1](#).

10. PARTICIPANT COMPLETION/DISCONTINUATION OF STUDY INTERVENTION/ WITHDRAWAL FROM THE STUDY

10.1. Completion

A participant will be considered to have completed study vaccination if he or she has received the vaccination on Day 1, or if he or she has received the vaccination on Day 1 and Day 365 (Month 12)/Day 730 (Month 24)/Day 1,095 (Month 36), as applicable, in case of Revaccination Subcohort participants.

A participant will be considered to have completed the study if he or she has completed all assessments at the final visit.

The end of the study is defined as the last participant's last visit.

10.2. Discontinuation of Study Vaccine/Withdrawal from the Study

Discontinuation of Study Vaccine

A participant's study vaccination must be discontinued if:

- The participant withdraws consent to receive study vaccination.
- The investigator believes that for safety reasons or reactogenicity reasons (eg, AE) it is in the best interest of the participant to discontinue study vaccination.

Study vaccine assigned to the participant who discontinued study vaccination may not be assigned to another participant.

Withdrawal from the Study

Each participant has the right to withdraw from the study at any time for any reason without affecting the right to treatment by the investigator. The investigator should make an attempt to contact participants who did not return for scheduled visits or follow-up. Although the participant is not obliged to give a reason for withdrawing prematurely, the investigator should make a reasonable effort to ascertain the reason(s) while fully respecting the participant's rights.

A participant will be withdrawn from the study for any of the following reasons:

- Lost to follow-up
- Withdrawal of consent
- Death
- Repeated failure to comply with protocol requirements
- Decision by the sponsor or the investigator to stop or cancel the study
- Decision by local regulatory authorities and IRB/IEC to stop or cancel the study
- If the randomization code is broken by the investigator or the study-site personnel.
If the randomization code is broken by the sponsor for safety reporting purposes, the participant should not discontinue further study vaccine administration (if applicable) and may remain in the study (if the randomization code is still blinded to the study-site personnel and the participant).

Any unnecessary study discontinuation should be avoided. Should a participant be withdrawn, all efforts should be made to complete and report the observations as thoroughly as possible. Whenever a participant is withdrawn from the study, independent of the reason, all procedures required at the final visit will be performed (see Section 9.1.6) and the major reason for which the participant was withdrawn must be stated. If the reason for withdrawal from the study is withdrawal of consent then no additional assessments are allowed.

If a participant is lost to follow-up, every reasonable effort must be made by the study-site personnel to contact the participant and determine the reason for discontinuation/withdrawal. The measures taken to follow-up must be documented.

When a participant withdraws before completing the study, the reason for withdrawal is to be documented in the eCRF and in the source document. Study vaccine assigned to the withdrawn participant may not be assigned to another participant. Additional participants will not be entered.

Participants who wish to withdraw consent from participation in the study will be offered a single exit visit for safety follow-up (prior to formal withdrawal of consent). They have the right to refuse.

Withdrawal from the Use of Samples in Future Research

The participant may withdraw consent for use of samples for research (refer to Section 16.2.5, Long-Term Retention of Samples for Additional Future Research). In such a case, samples will be destroyed after they are no longer needed for the clinical study. Details of the sample retention for research are presented in the ICF.

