3. STUDY DESIGN AND RATIONALE

3.1. Overview of Study Design

This is a multi-center, randomized, double-blind, placebo-controlled Phase 2b proof-of-concept study in male and female participants aged ≥ 65 years who are in stable health. A target of up to 5,800 participants (Cohort 1) will be enrolled and randomized in parallel in a 1:1 ratio to 1 of 2 groups to receive active study vaccine (Group 1) or placebo (Group 2) intramuscularly (Table 2).

Based on the primary analysis of safety and immunogenicity results from Cohort 2 in Study VAC18193RSV1004 (immunogenicity including, but not limited to RSV neutralizing antibodies), a sponsor committee has selected the study vaccine dose and regimen to be used in this study. In making the selection, additional factors such as data from other assays, cost of goods, and ease of administration were also taken into account.

The study comprises administration of an Ad26.RSV.preF/RSV preF protein mixture (or placebo) to be administered as a single injection on Day 1. After vaccination, participants will be followed for symptoms that could indicate an ARI until the end of the RSV season. The end of the first NH RSV season for the onset of an ARI is defined as 20 March 2020 (due to the coronavirus disease 2019 [COVID-19] pandemic, Amendment 2), the end of the second NH RSV season for the onset of an ARI will be defined as 17 May 2021, and the end of the third NH RSV season for the onset of an ARI will be defined as 15 April 2022^a. The end of the SH RSV season is country/territory-specific and will be specified to the sites prior to the start of dosing in the SH. Study progression

^a The defined end-of-season dates for the second and third NH RSV season may be updated in case there would be indications of a shift in season.

beyond the first and second RSV seasons is conditional on the results obtained at the end of each of these RSV seasons.

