When any participant experiences any symptom of ARI, the following will take place:

- Participants should contact the site as soon as possible to notify the site of any symptoms suggesting an ARI (such as rhinitis, nasal congestion, sore throat, cough, etc.), or the site should contact the participants if ARI symptoms are recorded in the eDiary. During this telephone or telemedicine contact, the site may confirm if the reported symptoms qualify as an ARI episode, in order to determine whether to proceed with the ARI procedures. The participant will then be reminded to:
 - Complete the eDiary including the RiiQ ([Attachment 5](#)) and Impact on Daily Activities Scale ([Attachment 11](#), as part of the Combined Impact Assessment), and thermometer readings every evening (preferably), beginning on the evening of the day of symptom onset (ARI Day 1) until the ARI episode resolves. The eDiary will also ask participants to complete the PGI-H, the PGI-S, the PGI-C, and the Return to Usual Health question ([Attachment 7](#), as part of the Combined Impact Assessment). (Note that the PGI-C and the Return to Usual Health question will not be completed on ARI Day 1). A resolved ARI episode is defined as 2 consecutive days with no symptoms listed on the RiiQ Symptom Scale or, for participants who have RiiQ symptoms present at baseline (assessed pre-vaccination for the first RSV season, at the Day 365 [Month 12] visit for the second RSV season [pre-vaccination if applicable], and at the Day 730 [Month 24] visit for the third RSV season), 2 consecutive days where all symptoms on the RiiQ Symptom Scale have returned to the severity level reported at baseline.

If a participant is unable to complete the eDiary, study staff can collect information on the participant's symptoms and temperature, by contacting the participant by telephone or telemedicine contact (or visit the participant at home), reading the questions aloud to the

participant and entering the participant's responses on the site's eDevice on the participant's behalf.

- Collect a midturbinate nasal swab at home on the day of symptom onset or the day thereafter (ARI Days 1-2). If the participant requires it, the participant's caregiver can assist the participant to collect the midturbinate nasal swabs.
- Ensure the midturbinate nasal swabs collected at home are provided to the study staff within 4 days (preferably) after collection.

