9.1.6. Early Withdrawal – Early Exit Visit

For those participants who are unable to continue participation in the study until the final visit, but who do not withdraw consent, an early exit visit will be conducted. In the event of early withdrawal from the study, all procedures as required at the end of the RSV season (see Section 9.1.4 and Section 9.1.5) will be performed.

The early exit visit will be conducted by telephone or telemedicine contact.

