11.1. Analysis Sets

Vaccination assignment will follow the as-treated principle.

- The Full Analysis Set (FAS) will include all randomized participants with a documented vaccine administration, regardless of the occurrence of protocol deviations. The FAS is the primary safety population. The analysis of solicited and unsolicited AEs after the Day 1 vaccination will be restricted to a subset of the FAS (ie, the Safety Subset).^a The analysis of solicited and unsolicited AEs after revaccination on Day 365 (Month 12)/Day 730 (Month 24)/Day 1,095 (Month 36) will be restricted to participants of the Revaccination Subcohorts that are part of the FAS.
- The Per-protocol Immunogenicity (PPI) population will include all randomized and vaccinated participants, for whom immunogenicity data are available. Samples taken after a participant experienced a major protocol deviation expecting to impact the immunogenicity outcomes will be excluded from the PPI. The list of major protocol deviations to be excluded from the immunogenicity analysis will be specified in the Statistical Analysis Plan (SAP) or major protocol deviation criteria document which will be finalized before database lock and unblinding. The analysis of immunogenicity will focus on 2 subsets of the PPI, ie, the Immuno Subset and the Revaccination Subcohorts.

In addition, for participants who experience a natural RSV infection (based on RT-PCR, or other sources), samples taken after the natural infection will not be taken into account in the assessment of the immunogenicity.

The PPI population is the primary immunogenicity population. For key tables, sensitivity immunogenicity analyses will also be performed on the FAS, including participants for whom immunogenicity measures are available. Excluded samples might be taken into account as well in the sensitivity analysis.

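### Section 10.2 withdraws repeated non-compliers from the study; where Day 1 is the only dose this spares no exposure and ends efficacy and safety follow-up, leaving both the PPE and the FAS incomplete for them

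*Protocol*

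**What the plan says.** Section 10.2 has two lists. One covers stopping study vaccine. The other opens with "A participant will be withdrawn from the study for any of the following reasons" and includes "Repeated failure to comply with protocol requirements". Non-compliance appears only on the second list, and no threshold is given for how much of it triggers withdrawal. The same section adds that "Any unnecessary study discontinuation should be avoided".

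Section 3.1 describes a regimen (active mixture "or placebo) to be administered as a single injection on Day 1"). Later doses are given only in the Revaccination Subcohorts, about 750 participants according to Section 11.2.4.

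After withdrawal without withdrawal of consent, Section 9.1.6 provides one exit visit: "The early exit visit will be conducted by telephone or telemedicine contact". Section 11.4.1.1 ends the follow-up time of a discontinued non-case at the last contact. Section 11.4.3.1 excludes participants who discontinued before the Day 365 visit from the Season 2 analysis, and those who discontinued before the Day 730 visit from the Season 3 analysis.

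On safety, Section 9.2.4.1 states "For all participants, SAEs will be collected from administration of study vaccine on Day 1 until the end of the first RSV season" (or for 6 months, if later). Deaths and vaccine-related SAEs are collected to the end of each participant's own study period.

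Section 11.1 says the FAS "will include all randomized participants with a documented vaccine administration, regardless of the occurrence of protocol deviations". The PPE leaves out participants with major deviations expected to affect efficacy. Section 11.4.1.1 repeats the primary model on the FAS.

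**The concern.** For a participant with no further dose to come, leaving the study protects them from nothing. It only stops observation. Compliance here means twice-weekly eDiary entries, daily entries during an ARI, self-collected swabs and site visits, in adults aged 65 and over. Repeated lapses may reflect frailty or illness, which the protocol itself sets out to relate to RSV incidence and severity (Section 11.7). The censoring that follows may therefore be informative.

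The analysis plan already deals with non-compliance through the PPE definition, with the FAS as the wider set. A rule that also ends observation leaves the FAS without data on these people after withdrawal. It shortens their SAE and death follow-up and, if they leave early, takes them out of the durability comparisons. The protocol states no benefit in return. Because no threshold is set, sites may also apply the rule differently.

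**Working it through.** **1. What withdrawal changes.** For participants outside the Revaccination Subcohorts:

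| Item | If kept in the study | After withdrawal under 10.2 |
|---|---|---|
| Further vaccine exposure | None (Day 1 only) | None |
| ARI surveillance | To end of season | Stops |
| New SAEs and deaths | Actively collected in the stated windows | One remote exit contact, then no active collection |
| SAEs open at discontinuation | Followed | Still followed (12.3.2) |
| Person-time in PPE and FAS | To event or end-of-season visit | To last contact |
| Season 2 / Season 3 analyses | Included | Excluded if before Day 365 / Day 730 |

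Revaccination Subcohorts: 240 (A) + 270 (B) + 240 (C) = 750, and 750 / 5,800 = 13%. The first row does not apply to them.

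**2. The protocol's own figures.** Inputs from Section 11.2.1: 2,750 per arm, 10% exclusions, placebo incidence 0.75%, VE 70%, one-sided 5%.

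- Placebo cases: 2,750 × 0.9 × 0.0075 = 18.56. Vaccine cases: 18.56 × 0.3 = 5.57. Total 24.1, against 26 stated. With 2,900 per arm the total is 25.4; with 2,750 and no exclusions it is 26.8.
- Power from an exact conditional binomial test on the case split, averaged over a Poisson total, single analysis at 5%: 81.7%, against 80% stated.

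The stated figures are reproduced closely enough to use as a base.

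**3. Events in the unobserved time (assumed rates).** The protocol gives no rate for this kind of withdrawal. Assume 1% to 5% (55 to 275 of 5,500), at mid-season on average.

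Events in the lost time = 26 × share × 0.5 × relative risk.

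- Relative risk 1: 26 × 0.01 × 0.5 = 0.13, up to 26 × 0.05 × 0.5 = 0.65.
- Relative risk 3: 0.39 up to 1.95.

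These are ceilings on what retention could recover, because a retained non-complier may not provide a swab.

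**4. Power (assumed losses beyond the planned 10%).**

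| Withdrawn per arm | Season lost | Expected cases | Power |
|---|---|---|---|
| 0% | – | 24.1 | 81.7% |
| 1% | half | 24.0 | 81.5% |
| 5% | half | 23.5 | 80.7% |
| 10% | all | 21.7 | 77.4% |

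**5. Bias in VE (all inputs assumed).** Let 5% of each arm be non-compliers with relative risk r, a share w of the arm be withdrawn from among them, and half a season be lost. With b the rate in compliers:

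observed rate = b × [0.95 + r(0.05 − w) + 0.5rw] / (1 − 0.5w).

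For r = 3:

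- w = 5%: 1.025b / 0.975 = 1.0513b.
- w = 2%: 1.07b / 0.99 = 1.0808b.

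Ratio of the two: 0.9727.

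- True VE 70%: 1 − 0.3 × 0.9727 = 70.8% if more are withdrawn on vaccine; 1 − 0.3 / 0.9727 = 69.2% if more are withdrawn on placebo.
- True VE 0%: +2.7% and −2.8%.
- Equal w in both arms: the factors cancel and VE is unbiased in this rate model.

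**The case against.** The case for leaving the text alone has several sound parts.

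- **The FAS still works as a check.** A reader might infer that the FAS cannot test the PPE exclusions at all. The text does not support that. The FAS restores deviators who stayed in the study, cases in the first 14 days, early discontinuers, and all time before withdrawal. Only the time after withdrawal is missing.
- **The two groups need not coincide.** A reader might also assume that those withdrawn for non-compliance are the people the PPE excludes. Section 11.1 does not say so. Someone withdrawn after Day 14 may sit in both sets with the same follow-up.
- **Exposure is at stake for some.** For the roughly 750 revaccination participants, withdrawal can prevent further doses, so the point is limited to the others.
- **Retention does not guarantee ascertainment.** A primary case needs RT-PCR confirmation, and telephone contact yields symptoms and temperature only. Retained non-compliers may add apparently event-free time. At 5% withdrawn for half a season that time is 0.05 × 0.5 = 2.5% of the total. If no case were detected in it, each arm's rate would read 2.5% lower, and VE would be unchanged if the shares were equal by arm.
- **Mitigation exists.** Staff are to contact participants after a missed diary, open SAEs are followed, and the sponsor evaluates spontaneously reported late safety information (12.3.1). It would be too absolute to say that every later SAE or death is lost; what ends is active collection.
- **The numbers are small and assumed.** The 10% allowance covers drop-out and deviations for power.

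All of this narrows the point. None of it gives a reason to end observation of someone who has not withdrawn consent. The general instruction to avoid unnecessary discontinuation does not override a rule worded as mandatory, and the 10% allowance protects power, not safety follow-up or against informative censoring.

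**Conclusion.** The point holds in limited form. For participants whose only dose is on Day 1, the non-compliance bullet causes an avoidable and possibly informative loss of efficacy and safety follow-up, with no stated benefit. The loss falls on the PPE and the FAS alike, so the FAS analysis is weakened for these participants, not defeated.

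The size is unknown because no withdrawal rate is given. With 1% to 5% withdrawn at mid-season, 0.13 to 1.95 of 26 expected Case Definition #2 events fall in the unobserved time, and 55 to 275 people lose the rest of their active SAE and death follow-up. VE moves by less than one point from 70% under an assumed 5% versus 2% imbalance and up to three times the risk. It does not move if withdrawal is equal by arm. A reader might conclude that the sample size or the primary conclusion is in doubt; these figures do not support that. The change is worth making because it is cheap and the loss is avoidable.

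**What to change.** Delete the non-compliance bullet from the reasons for withdrawal from the study in Section 10.2. State that such participants, unless they withdraw consent, stay in follow-up for SAEs, deaths and, as far as they cooperate, ARI events. Section 9.1.1 already supplies the route: "If a participant is unable to complete the eDiary, study staff can collect information on the" participant's symptoms and temperature, by telephone, telemedicine or home visit. Swabs would be taken where obtainable. Deviations continue to be handled through the PPE definition, and decisions on further vaccination stay under the existing rules.

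Reasons for withdrawal are already recorded in the eCRF, so withdrawals made on this ground can be tabulated by arm without new data collection.

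Cost: one bullet, one added sentence and some extra contacts. The downside is less complete ARI ascertainment in these participants, which may add under-observed person-time to the FAS.

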In the Revaccination Subcohorts, all participants will receive active study vaccine at the time of revaccination (Ad26.RSV.preF/RSV preF protein mixture or the individual vaccine components as shown in [Table 2](#)). The blinding for the study vaccine received on Day 1 will be maintained for site and participants until the database lock for the final analysis of the considered cohort, except for Revaccination Subcohorts A and B, who will be unblinded to the Day 1 vaccination prior to re-randomization to the third vaccination: participants who received active vaccine on Day 1 will complete the study at that time, participants who received placebo on Day 1 will be re-randomized to receive either Ad26.RSV.preF/RSV preF protein mixture or the individual vaccine components in a blinded fashion.

From the primary analysis onwards, group level results may be shared externally as needed, however, efforts will be made to preserve the blinding to the individual participant allocation.

The investigator may in an emergency determine the identity of the intervention by contacting the IWRS. While the responsibility to break the intervention code in emergency situations resides solely with the investigator, it is recommended that the investigator contact the sponsor or its designee if possible to discuss the particular situation, before breaking the blind. Telephone contact with the sponsor or its designee will be available 24 hours per day, 7 days per week. In the event the blind is broken, the sponsor must be informed as soon as possible. The date, time, and reason for the unblinding must be documented by the IWRS, in the appropriate Section of the eCRF, and in the source document. Documentation received from the IWRS indicating the code break must be retained with the participant's source documents in a secure manner. The investigator is advised not to reveal the study vaccine assignment to the study-site personnel or sponsor personnel/sponsor representative.

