If the randomization code is broken by the investigator or the study-site personnel, the participant must discontinue further study vaccine administration (if applicable) and must be followed as appropriate until the end of the RSV season (refer to [Section 10.2](#) for details). If the randomization code is broken by the sponsor for safety reporting purposes, the participant should not discontinue further study vaccine administration (if applicable) and may remain in the study (if the randomization code is still blinded to the study-site personnel and the participant).

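### Sections 5 and 10.2 give opposite instructions after a code break by the site: one keeps the participant in follow-up to season end, the other withdraws the participant from the study

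*Protocol*

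**What the plan says.** Protocol Section 5 (Blinding) provides for individual emergency unblinding: "The investigator may in an emergency determine the identity of the intervention by contacting the IWRS". If the investigator or site staff break the code, "the participant must discontinue further study vaccine administration (if applicable) and must be followed as appropriate until the end of the RSV season". A cross-reference to Section 10.2 for details follows directly.

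Section 10.2 has two lists. The first, on discontinuation of study vaccine, does not mention a code break. The second, on withdrawal from the study, opens with "A participant will be withdrawn from the study for any of the following reasons", and its last entry is "If the randomization code is broken by the investigator or the study-site personnel". For anyone withdrawn, whatever the reason, "all procedures required at the final visit will be performed", unless consent has been withdrawn. Section 9.1.6 adds: "The early exit visit will be conducted by telephone or telemedicine contact".

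For a code break by the sponsor for safety reporting the two sections agree that the participant may stay in the study. The conflict is confined to breaks by the investigator or site.

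**The concern.** The two instructions are mandatory and incompatible, and the cross-reference sends a site from one to its opposite. Sites that act on Section 5 and sites that act on Section 10.2 will treat the same event differently.

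The Section 10.2 reading costs data. A withdrawn participant leaves ARI surveillance, so a later RSV episode cannot be detected, and new SAEs are no longer collected. Because the protocol foresees investigator unblinding in an emergency, the trigger will usually be a medical event. Loss of follow-up at that moment is therefore potentially related to the participant's health, and it falls on people whose later safety course is of particular interest.

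**Working it through.** The protocol gives no figure for code breaks, so there is nothing of its own to reproduce. The check is a comparison of text, followed by one bound on size.

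**Side by side, for a break by the investigator or site**

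| Question | Section 5 | Section 10.2 |
|---|---|---|
| Stays in follow-up? | Yes, to season end | No, withdrawn from the study |
| Further study vaccination? | Stopped, if applicable | Not in the vaccine-discontinuation list |

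This is current text, not the amendment history, and no other section settles it. Section 10.2 also asks that unnecessary discontinuation be avoided, which fits Section 5 better than its own list. Under Table 2 most Cohort 1 participants receive a single injection on Day 1. For them no vaccination is left to stop, and withdrawal ends only observation.

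**What withdrawal does to the data**

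- Efficacy: under Section 11.4.1.1 a participant who discontinues without an event contributes time only to the date of last contact. Later cases are never observed.
- Safety, what ends: under Section 12.3.1 vaccine-related SAEs and deaths are collected to the end of each participant's study period. Withdrawal brings that end forward.
- Safety, what continues: exit procedures (Sections 9.1.6 and 10.2), follow-up of SAEs unresolved at discontinuation (Section 12.3.2), and follow-up of clinically significant abnormalities that persist at early withdrawal (Section 9.2.4.1).

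**A bound on the effect on case counts**

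Inputs from Section 11.2.1: Case Definition #2 incidence of 0.75% on placebo per season, and VE of 70%.

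- Incidence on vaccine: 0.75% × (1 − 0.70) = 0.225%.
- Average over two equal arms: (0.75% + 0.225%) / 2 = 0.4875%.
- Code breaks needed to lose one expected case: 1 / 0.004875 ≈ 205.

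This assumes that every unblinded participant still had a whole season at risk and had the average risk. Less time remaining raises the number needed. A higher than average risk among people with a medical emergency lowers it in proportion: at twice the average risk, an assumption made only for illustration, it would be about 103.

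**The case against.** The strongest reply is that little is lost. The event that prompted the unblinding remains covered: final-visit procedures are done, unresolved SAEs are followed to an outcome, and Section 12.3.1 has the sponsor evaluate safety information that investigators report after the collection window. Code breaks are likely to be few, and the bound above shows that the primary analysis would hardly notice them. On size this is right, and it limits the point to new events and to consistency. It does not remove the contradiction.

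Four stronger readings are tempting, and the protocol does not support them.

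- A reader might infer that safety data stop at withdrawal. They do not: only the collection of new events ends.
- A reader might note that 26 Case Definition #2 cases are expected, so that each lost case is about 1/26, or 4%, of the events. That figure leaves out how rarely an unblinded participant would go on to become a case.
- A reader might apply Section 10.2 to Revaccination Subcohorts A and B, who are unblinded to Day 1 before the third vaccination. Section 5 treats this as a planned exception with its own consequences: Day 1 active recipients complete the study and placebo recipients are re-randomized. It is not a code break of the emergency kind.
- A reader might think that the unblinding date goes unrecorded or that these participants drop out of the Full Analysis Set. Section 5 already requires the date, time and reason to be documented, and Section 11.1 defines the FAS by randomization and documented vaccination regardless of protocol deviations.

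**Conclusion.** The contradiction is real and should be corrected. Sections 5 and 10.2 cannot both be followed after a code break by the investigator or site. Read as written, Section 10.2 ends ARI surveillance, collection of new SAEs and accrual of person-time in participants probably unblinded for a medical reason.

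The expected effect on VE is small. That judgement rests on the protocol's incidence and efficacy assumptions and on code breaks being uncommon, which is likely but not stated. No difference between arms can be shown from the document. The point does not call the primary result into question. It concerns uniform conduct across sites and avoidable loss of new safety and efficacy events.

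**What to change.** Remove the code break by the investigator or site personnel from the reasons for study withdrawal in Section 10.2, so that these participants remain in ARI surveillance and SAE follow-up as Section 5 requires. The cross-reference from Section 5 will then lead to a consistent rule.

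Separately, the sponsor must reconcile the two sections on further study vaccination after such a break: Section 5 states a consequence that the vaccine-discontinuation list in Section 10.2 does not contain. Which wording should stand is for the sponsor to decide.

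The cost is a short text change in an amendment and a note to sites. For participants affected it means continuing the surveillance already scheduled for them.
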